Each cohort will consist of two treatment arms. Cohort progression for each treatment arm will be managed independently of the other treatment arm. For example, if data from the *P. falciparum* cohort (1A) do not meet the success criteria or are inconclusive, but the data from the *P. vivax* cohort (1B) do meet the success criteria, then the *P. vivax* arm may continue to explore reducing levels of SJ733 exposure according to Figure 1 (cohort 2B and 3B), while the *P. falciparum* initial cohort of the study will be expanded or terminated. Established antimalarial therapy will be given if a patient meets any of the defined treatment failure criteria. Finally, if one treatment arm meets the failure criteria, remaining patients who have not received treatment may be reassigned to the other treatment arm to improve statistical power.

Study Population

Men and women between the ages of 18 and 70 years with *P. falciparum* or *P. vivax* malaria monoinfection living in Peru. 2-6 cohorts of adult patients (10 patients per cohort) with acute, uncomplicated *P. falciparum* or *P. vivax* malaria monoinfection. In total, there will be a minimum of 20 and a maximum of 60 patients.

3. Data Elements

Endpoints

Primary endpoints related to efficacy

For *P. vivax:* Crude Adequate Clinical and Parasitological Response (ACPR) at Day 14 defined as the absence of microscopically determined parasitemia (thick smear) on Day 14, irrespective of axillary temperature, in patients who did not previously meet any of the criteria of early treatment failure, late clinical failure, or late parasitological failure.

For *P. falciparum:* Crude Adequate Clinical and Parasitological Response (ACPR) at Day 14 defined as the absence of microscopically determined parasitemia (thick smear) on Day 14, irrespective of axillary temperature, in patients who did not previously meet any of the criteria of early treatment failure, late clinical failure, or late parasitological failure.

Success criterion: Crude ACPR on Day $14 \ge 80\%$ (equivalent to $\le 20\%$ recurrence).

Primary endpoints related to safety and tolerability up to Day 42

- Incidence, severity, drug-relatedness, and seriousness of adverse events
- Proportion of patients with clinically significant abnormal laboratory values including changes from baseline (biochemistry and hematology)
- Proportion of patients with clinically significant abnormal vital signs including changes from baseline

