The overall study design is to demonstrate proof of concept and serves as an exploratory study. It is not intended to demonstrate superiority or non-inferiority against a control. Rather the goal is to establish preliminary data for planning future studies and to assess whether the SJ733 is safe and the observed curative rate equals or exceeds 80%. As such, there will be no statistical testing of hypotheses. This exploratory Proof of Concept study uses a fixed clinical safety and parasitological responses (primary endpoints) defined as the absence of any drug-related SAE or microscopically determined parasitemia 14-days after initiation of therapy in \geq 80% patients who did not violate any of the inclusion/exclusion criteria.

General Approach

The overall study design involves two cohorts receiving SJ733 doses (600 mg and 300 mg) with and without cobicistat (150 mg) as cohorts. Data subsets (eligible, evaluable and completer) will be used in the potential comparisons.

The primary analytic approaches will be descriptive. All data will be summarized descriptively for the appropriate analysis sets defined below: Continuous variables by descriptive statistics (number of patients [n], mean, standard deviation [SD], minimum, median, maximum); categorical data by absolute and relative frequencies (n and %) or contingency tables.

While this is a proof of concept, exploratory study, any potential comparisons between dose cohorts will be informative. Potential longitudinal data will be described as graphical summaries presented by each group. Unless indicated otherwise, summary statistics will be reported for observed data only, by dose cohort. Missing data will not be imputed. If a baseline value is missing, no change from baseline will be calculated.

Baseline is defined as the last observation prior to the administration of study medication.

SAS v9.4 or higher will be used for all analyses and a significance level of 0.05 will be used for all statistical tests.

Primary Analysis (Efficacy)

Primary analyses will be conducted across the two cohorts and by the two cohorts. Estimates will be presented with 95% confidence intervals.

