The primary efficacy endpoints will be summarized descriptively, across the two cohorts and by the two cohorts. A statistical test will not be performed on the Crude ACPR on Day 14. Achieving a rate of 80% will be the decision rule for cohort dose phase. For future study planning, a one-sample z-test will be used to compare the rate of success, as defined by the Crude ACPR on Day 14, to the hypothesized rate of 80%.

Secondary efficacy variables will be summarized descriptively (by cohort; on Days 0, 14, 42) with proportions, means, and medians. To inform future studies, all estimates will be presented with 95% confidence intervals ($1.96 \pm$ margin of error). Graphical summaries will be used to describe changes in efficacy endpoints over time.

Exploratory Analysis

Exploratory model-based analyses will be performed as data allows. These will include model-based analyses of PK, PD and PK/PD.

Safety Analysis

Adverse events (AEs) will be summarized in Listing 9: Cumulative Summary of Adverse Events. The listing will include the following information: Patient ID, AE Description, Start Date, Stop Date, Special Interest, Severity, Relationship to Study Drug, Action Taken, Outcome of AE, Expected AE, and if the AE was a Serious Adverse Event (SAE).

Laboratory values that fall outside a clinically accepted reference range must be evaluated and commented on by the Investigator and graded according to the DMID Toxicity Scale for Determining Severity of Adverse Events (Protocol Attachment 3, Section 8.1.2).

All related AEs, AEs with outcome death, AEs leading to permanent discontinuation of treatment, SAEs and related SAEs will be summarized in Listing 10: Cumulative Summary of Serious Adverse Events. The listing will include the following information: Patient ID, Age, Sex, Dose, SAE Description, Start Date, Stop Date, SAE Category, and Relationship to Study Drug.

Treatment related AEs are those rated by the Investigator as "definite", "probable", "possible". In case relationship is unknown or missing the worst case will be assumed and the AE will be considered to be drug related

Planned Interim Analyses

Interim analyses will be made to review parasite reduction, adverse events, and clinical laboratory data. Following review, a decision on cohort progression will be made. However, as this is an exploratory study no formal analyses with adjustments for type I error are planned.

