The following rules will be used as general guidelines to aid the decision of cohort progression:

- Curing ≥8/10 patients without any repeated drug-related SAEs then explore lower dose;
- Curing 6/10 or 7/10 patients without any repeated drug-related SAEs would be inconclusive and as a result we would expand the treatment arm;
- Curing $\leq 5/10$ is failure which would stop the trial in Cohort 1.

Strategies to Minimize Bias

Given the nature of the study, issues related to randomization/blinding/masking do not apply.

Sample Size Justification

The sample size for this exploratory Proof of Concept study was based on primary efficacy hypothesis. A one-sample z-test will have at least 85% power to detect the difference between the hypothesized curative rate (80%) with an alternative curative rate of 98%, assuming a one-sided significance level of 0.05, when the sample size is 20. All primary analyses will pool parasite arms within cohort dose. As such, a sample size of 10 patients per dose cohort arm was considered adequate to gain efficacy and safety data in patients with *P. falciparum* and *P. vivax* or to permit evaluation of MIC and MEC as

per similar studies conducted. If patients drop out for reasons unconnected to efficacy, attempts will be made to replace them to try to ensure the maximum number in each cohort.

5. Planned Tables, Listings, and Figures.

Number	Tables*
	*Tables will be provided overall and by cohort
Table 1	Patient Status
Table 2	Patient Demographics and Baseline Characteristics
Table 3	Malaria Sign and Symptoms
Table 4	Clinical Laboratory Summary
Table 5	Vital Signs
Table 6	12-LEAD ECG Summary
Table 7	Primary Endpoint
	Figures
Figure 1	Patient Status
Figure 2a	Efficacy: Asexual Parasite Count Over Time Up to Day 42 – Microscopist Report 1
Figure 2b	Efficacy: Asexual Parasite Count Over Time Up to Day 42 – Microscopist Report 2
Figure 3-	qPCR Values Over Time Up to Day 42
Figure 4a	Crude ACPR – Microscopist Report 1
Figure 4b	Crude ACPR – Microscopist Report 2
Figure 5	eDISH Plot
Figure 5a	Liver Testing by Patient
Figure 6	Total Bilirubin Lab Result (mg/dL) Over Time
Figure 7	Albumin Lab Result (g/dL) Over Time
Figure 8	ALT/SGPT Lab Result (U/L) Over Time
Figure 9	AST/SGOT Lab Result (U/L) Over Time
Figure 10	LDH Lab Result (U/L) Over Time
Figure 11	Alkaline Phosphate Lab Result (U/L) Over Time
Figure 12	Creatine Kinase Lab Result (mg/dL) Over Time
Figure 13a	Creatine Kinase Lab Result (mg/dL) Over Time for Males

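### The SAP's only confidence-interval formula is invalid, and the normal-approximation interval it implies is unsuitable for Day 14 crude ACPR at 10 to 40 patients

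*Combined protocol and SAP*

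**What the plan says.** The primary efficacy endpoint (SAP section 3, Endpoints) is binary: "Crude Adequate Clinical and Parasitological Response (ACPR) at Day 14 defined as the absence of microscopically determined parasitemia (thick smear) on Day 14", in patients who had not already failed. The benchmark is 80% (section 4, Primary Analysis): "Achieving a rate of 80% will be the decision rule for cohort dose phase".

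The Primary Analysis section opens with "Estimates will be presented with 95% confidence intervals" and names no method. The paragraph on secondary efficacy variables then gives the SAP's only formula: "all estimates will be presented with 95% confidence intervals ($1.96 \pm$ margin of error"). The same section adds a test against 80%: "For future study planning, a one-sample z-test will be used to compare the rate of success".

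Three sample sizes follow from the text:

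- **10 per parasite arm.** Study Population gives "2-6 cohorts of adult patients (10 patients per cohort"), and Study Design defines success separately for each treatment arm.
- **20 per dose.** Sample Size Justification says "All primary analyses will pool parasite arms within cohort dose".
- **About 40.** Primary Analysis also summarises across the two cohorts.

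The power calculation sets the 80% rate against "an alternative curative rate of 98" percent.

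**The concern.** As printed, the formula centres every interval on the normal quantile and not on the estimate, so it cannot be programmed. A programmer would most likely repair it to estimate ± 1.96 × SE.

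For a proportion, that interval relies on a normal approximation that fails when n is small and the rate is near 100%, which is where the design alternative puts this trial. Its width is zero when all patients respond, its upper limit can pass 100%, and it covers the true rate much less often than 95%.

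The trial is descriptive, and the SAP says the intervals are there to inform future studies. The estimate and its interval are therefore the main product. An interval lying wholly above 80% could be read in Phase 2b planning as evidence that the rate exceeds 80%, when the data do not support that at the stated confidence.

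**Working it through.** **Inputs.** Benchmark 80%, alternative 98%, N = 20 and one-sided 0.05 come from Sample Size Justification. The sizes 10, 20 and 40 are derived above (2 × 10 = 20; 2 × 20 = 40).

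**1. The SAP's own figure.** Power of the one-sample z-test with null variance in the critical value:

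Φ[(0.98 − 0.80 − 1.645 × √(0.80 × 0.20/20)) / √(0.98 × 0.02/20)] = 85.3%.

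The stated figure of at least 85% reproduces and is not in dispute.

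**2. The formula read literally.** The largest Wald half-width at n = 10 is 1.96 × √(0.25/10) = 0.31. The interval would then run from 1.65 to 2.27, which is impossible for a proportion.

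**3. The formula repaired to Wald,** k/n ± 1.96 × √[(k/n)(1 − k/n)/n]:

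- 19/20: 0.95 ± 1.96 × √(0.95 × 0.05/20) = 0.95 ± 0.0955
- 36/40: 0.90 ± 1.96 × √(0.90 × 0.10/40) = 0.90 ± 0.0930
- 10/10, 20/20 and 40/40: half-width 0

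Clopper-Pearson limits come from beta quantiles; Wilson uses z = 1.96.

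| Result | Wald | Clopper-Pearson | Wilson |
|---|---|---|---|
| 10/10 | 100–100% | 69.2–100% | 72.2–100% |
| 19/20 | 85.4–104.6% | 75.1–99.9% | 76.4–99.1% |
| 20/20 | 100–100% | 83.2–100% | 83.9–100% |
| 36/40 | 80.7–99.3% | 76.3–97.2% | 76.9–96.0% |
| 40/40 | 100–100% | 91.2–100% | 91.2–100% |

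At 10/10, 19/20 and 36/40 Wald excludes 80% and the other two include it. The Wald upper limit exceeds 100% at 8/10 and 9/10, at 17/20 to 19/20, and at 37/40 to 39/40.

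**4. Chance of a zero-width interval,** pⁿ:

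| True rate | n = 10 | n = 20 | n = 40 |
|---|---|---|---|
| 80% | 10.7% | 1.2% | 0.01% |
| 90% | 34.9% | 12.2% | 1.5% |
| 95% | 59.9% | 35.8% | 12.9% |
| 98% | 81.7% | 66.8% | 44.6% |

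**5. Wald coverage,** the sum of Binomial(n, p) probabilities over all k whose interval contains p (nominal 95%):

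| True rate | n = 10 | n = 20 | n = 40 |
|---|---|---|---|
| 80% | 88.6% | 92.1% | 90.5% |
| 90% | 65.0% | 87.6% | 91.4% |
| 95% | 40.0% | 63.9% | 86.8% |
| 98% | 18.3% | 33.2% | 55.3% |

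**6. Chance that the lower limit exceeds 80% when the true rate is exactly 80%** (nominal 2.5%):

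- Wald: P(X = 10) = 10.7% at n = 10; P(X ≥ 19) = 6.9% at n = 20; P(X ≥ 36) = 7.6% at n = 40. At the intermediate n = 30 it is 4.4%, so the excess varies with n.
- Clopper-Pearson: 0%, 1.2% and 0.8% at n = 10, 20 and 40.
- Wilson: 0%, 1.2% and 2.8%.

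**7. Minimum coverage of the replacements,** true rates 80% to 98% in steps of 0.1 point, n = 10, 20, 40:

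- Clopper-Pearson: 97.5%, 96.1%, 95.3%.
- Wilson: 89.5%, 89.9%, 92.2%.

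**The case against.** **Wald is inferred.** The formula is probably a slip, and the planned z-test is weak support for Wald: the stated power reproduces with the null variance, and inverting that form of the test gives Wilson. This stands. The inference rests on the 1.96 and the ± form. If Wald was not meant, the SAP still gives no usable interval method for its primary endpoint.

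**Placement.** The formula stands in the secondary-efficacy paragraph. It reaches Day 14 crude ACPR because it is worded for all estimates and because the primary-analysis sentence offers nothing else. That reading is plausible, though not certain.

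**The n = 10 figures are the most striking, and primary analyses pool the arms.** This is a fair point on emphasis. However, success is defined per arm, and the defects remain at n = 20 and n = 40.

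**98% is the most favourable rate.** The chance of zero width falls quickly at lower rates, as step 4 shows. At a true 80% the problem is mainly the lower limit lying above 80% too often.

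**The z-test would sit beside the interval.** At 10/10 and 36/40, z = 1.58, which is not significant at one-sided 0.05 (critical value 1.645). This lessens the risk of misreading, but an interval and a test that disagree are themselves a reason to name a method. At 19/20, z = 1.68 and a one-sided test rejects, with an exact type I error of 6.9%; changing the interval does not alter that.

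**The study is exploratory.** No progression rule or sample size depends on the interval. This limits the consequence to reporting and later planning.

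**Conclusion.** The concern holds. The only interval formula in the SAP is wrong as printed, and no method is named for the primary endpoint. That much depends on no assumption.

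If the formula is repaired to Wald, the primary interval is unreliable in the range the trial was designed for. At a true 98%, coverage is 33.2% with 20 patients and 55.3% with 40. At a true 80%, the lower limit lies above the benchmark in 6.9% and 7.6% of trials, against a nominal 2.5%; with 10 patients it is 10.7%. These figures assume independent binomial responses and complete cohorts of 10, 20 and 40. The point should be fixed before reporting, but it does not affect cohort decisions.

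**What to change.** In Primary Analysis (Efficacy), replace the bracketed formula with: two-sided 95% Clopper-Pearson (exact) intervals for efficacy proportions, including Day 14 crude ACPR. Name the same method in the opening sentence on primary estimates. Wilson is acceptable if its lower minimum coverage (step 7) is accepted.

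For means, correct the expression to estimate ± critical value × SE. As added detail, name a method for medians and state whether intervals are reported per parasite arm, per dose with arms pooled, across doses, or at all three levels.

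The cost is one or two SAP sentences and no new data. The intervals become wider and, with Clopper-Pearson, somewhat conservative.

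### At n = 20 the planned one-sided 0.05 z-test of an 80% cure rate has an exact type I error of 6.9%, and the cut-off that does hold 5% has only 67% power.

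*Combined protocol and SAP*

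**What the plan says.** SAP section 4, Sample Size Justification, states: "A one-sample z-test will have at least 85% power to detect the difference between the hypothesized curative rate (80"%) and an alternative of 98%, "assuming a one-sided significance level of 0.05, when the sample size is 20". The 20 comes from two species arms of 10: "All primary analyses will pool parasite arms within cohort dose".

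Primary Analysis (Efficacy) says of the same endpoint: "A statistical test will not be performed on the Crude ACPR on Day 14". It makes an observed 80% the decision rule for the dose phase, and then adds: "For future study planning, a one-sample z-test will be used to compare the rate of success", the comparison value being 80%.

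The opening of section 4 says: "As such, there will be no statistical testing of hypotheses". General Approach, in the same section, says that "a significance level of 0.05 will be used for all statistical tests" and gives no side.

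On how the arms move through the study, section 2 (Study Design) says: "Cohort progression for each treatment arm will be managed independently of the other treatment arm".

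**The concern.** This is the only power calculation in the documents. It gives a level and a power side by side, as if both belonged to the same test. With 20 patients and rates of 80% and 98%, the number cured is a coarse count close to its ceiling: at 98%, only 20 × 0.02 = 0.4 failures are expected. A normal approximation cannot be relied on there, so the level and power have to be checked against the binomial distribution.

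Two things are at stake. The first is whether the stated justification for 20 patients is true. The second is how a result such as 19/20 would be described to those planning the next study. The wording adds to the difficulty. The SAP says in two places that there is no test, then plans one, and the general 0.05 could be read as two-sided.

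**Working it through.** **Inputs** (SAP section 4, Sample Size Justification): p0 = 0.80, p1 = 0.98, n = 20, one-sided level 0.05 (critical value 1.645).

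**Step 1. The plan's own figure.** Normal-approximation power:

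Φ[(p1 − p0 − 1.645·√(p0(1−p0)/n)) / √(p1(1−p1)/n)]

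= Φ[(0.18 − 1.645·√(0.16/20)) / √(0.0196/20)]

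= Φ[(0.18 − 0.1471)/0.0313] = Φ(1.05) = 85.3%.

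So the 85% reproduces. The same formula gives n = 19.9 for 85% power.

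**Step 2. Where the z-test rejects.** z = (x/20 − 0.80)/√(0.16/20), with √(0.16/20) = 0.0894.

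- 18/20: z = 1.118, no rejection.
- 19/20: z = 1.677 > 1.645, rejection (one-sided p = 0.047).
- 20/20: z = 2.236, rejection.

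**Step 3. Exact size and power of each cut-off.**

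- P(X = 20 | 0.80) = 0.8^20 = 0.0115. P(X = 19 | 0.80) = 20·0.2·0.8^19 = 0.0576. Their sum is 0.0692.
- P(X = 20 | 0.98) = 0.98^20 = 0.6676. P(X = 19 | 0.98) = 20·0.02·0.98^19 = 0.2725. Their sum is 0.9401.

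| Rule at n = 20 | Exact size at 80% | Exact power at 98% |
|---|---|---|
| 19/20 or more (the planned z-test) | 6.9% | 94.0% |
| 20/20 only | 1.2% | 66.8% |

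The next lower cut-off, 18/20, has size 20.6%. No cut-off at n = 20 therefore gives both size at or below 5% and power of at least 85%. Randomising at 19/20 to reach exactly 5% would use probability (0.05 − 0.0115)/0.0576 = 0.667. Power would be 0.6676 + 0.667·0.2725 = 84.9%, but such a test is not used in practice.

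**Step 4. Does the z-test variant matter?** With the estimated (Wald) variance the one-sided test still rejects at 19/20 or more. With a continuity correction it rejects only at 20/20. Each variant falls on one row of the table.

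**Step 5. Smallest n with both properties.** Below n = 14 an exact 5% test cannot reject. For n = 14 to 21 it needs every patient cured, and its power is at most 0.98^14 = 75.4%. At n = 22 it rejects at 21/22 or more:

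- size 0.8^22 + 22·0.2·0.8^21 = 0.0074 + 0.0406 = 4.8%;
- power 0.98^22 + 22·0.02·0.98^21 = 0.6412 + 0.2879 = 92.9%.

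**Step 6. Dependence on a full pooled 20.**

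- n = 19: 18/19 gives z = 1.606, so the z-test needs 19/19. Size is 0.8^19 = 1.4% and power is 0.98^19 = 68.1%.
- n = 10 (one unexpanded species arm at a dose): 10/10 gives z = 0.20/√0.016 = 1.58 and exact p = 0.8^10 = 0.107. The test cannot reject.

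**Step 7. If the general 0.05 is read as two-sided** (critical value 1.960). The test of Step 2 then needs 20/20, with exact power 66.8%. The normal-approximation power falls to Φ[(0.18 − 0.1753)/0.0313] = 56.0%. A 19/20 result has two-sided p = 0.094.

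**The case against.** The strongest reply is that nothing was miscalculated. The 85% is the standard approximation, 0.05 is a nominal level, and the planned z-test exceeds the promised power (94.0%). The 67% belongs to a stricter test that the SAP does not plan, and the gap between 6.9% and 5% is ordinary discreteness. The mid-p value at 19/20 is 0.0115 + 0.0576/2 = 0.040, close to the z-test's 0.047. All of this is right as far as it goes, and the choice between an exact and an approximate test is partly a preference. It does not make the stated 5% the actual error rate. An excess of 1.9 percentage points over the nominal level should be disclosed where the calculation is the sample-size justification.

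Secondly, nothing turns on the test. The study is exploratory, and progression follows the observed count (8/10 or more, 6 or 7, 5 or fewer). That stands, and it limits the consequence.

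Thirdly, the small-n cases are softened by other provisions. Replacement of dropouts will be attempted, inconclusive arms may be expanded, and untreated patients from a failed arm may be reassigned. These make 19 or 10 less likely but do not exclude them: replacement is not guaranteed and does not cover efficacy-related dropout. The SAP claims no power at n = 10.

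Finally, the sample-size section does say one-sided, and the statement for all tests gives no side. This is an ambiguity, not a contradiction. The no-test sentence can likewise be read as applying to progression only, but the SAP does not say so.

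**Conclusion.** The concern holds. At n = 20 the one-sided 5% level and the power of at least 85% are not both achieved by any non-randomised test of 80% against 98%. The planned z-test has 94.0% power at an actual level of 6.9%; the rule that holds 5% has 66.8% power at an actual level of 1.2%. The fault lies in the stated level, not in the arithmetic behind the 85%. The SAP's statements on whether Day 14 ACPR is tested also need reconciling.

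The figures assume independent patients, a full pooled 20 at one dose and a single cure rate shared by the two species. The consequence is confined to the planning statement and to the description of a result such as 19/20 (exact p = 0.069). No cohort progression decision is affected. It should be fixed, but it does not threaten the conduct of the trial.

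**What to change.** In Sample Size Justification and Primary Analysis (Efficacy), do one of the following:

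- Keep the z-test and state its exact properties at a pooled n = 20: rejects at 19/20 or more, type I error 6.9%, power 94% at a true rate of 98%.
- Replace it with an exact one-sided 5% binomial test and state: rejects at 20/20 only, type I error 1.2%, power 67%.

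Either way, add that a dose cohort holding a single arm of 10 cannot reject 80%. The first option avoids changing the test at a late stage: this SAP version is dated 11/04/2022, and its planned start of analysis was 05/2021.

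Reconcile the no-test sentences with the planned test, for example: no test is used for cohort progression; one descriptive test against 80% is reported for planning. In General Approach, say that the 0.05 is one-sided for this test.

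The cost is SAP wording only, with no extra patients. The downside is a less favourable stated figure, either the level (6.9%) or the power (67%).

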Cohort 2 will test whether pharmacoenhancement of SJ733 with cobicistat is required for clinical efficacy. If cohort 2 meets the success criteria, the trial will be complete. If data from cohort 2 are inconclusive, an adaptation will be triggered to use the same regimen for a larger number of patients in order to improve statistical power and more accurately classify a potential failure. If cohort 2 proves safe (no repeated drug-related SAE) but not efficacious (crude ACPR < 60%), an adaptation will be triggered to use an intermediate exposure of SJ733, obtained by pharmacoenhancement of a reduced dose of SJ733 (optional cohort 3). Due to the pharmacoenhancing effects of cobicistat, a co-dose of SJ733 (300 mg) + cobicistat (150 mg) is expected to yield a higher total plasma exposure (median AUC) of SJ733 than a dose of SJ733 (600 mg) alone (Figure 1). The increase in plasma exposure is expected to provide increased efficacy. While cohort 3 requires co-dosing with a pharmacoenhancer, if successful, this regimen would reduce the quantity of SJ733 required by two-fold, lowering cost of goods and potentially improving tolerability.

Cohorts 1a and 1b are expected to achieve roughly five-fold higher plasma exposure of (+)-SJ733 than Cohorts 2a and 2b. Thus, if Cohorts 1a and 1b prove efficacious but repeated drug-related adverse events are observed, the Investigator, DMC, and SRT may unanimously agree that no further patients should be recruited to Cohorts 1 but that patient recruitment to Cohorts 2 should still be pursued. In this scenario, the Investigator will assess the severity/intensity of the adverse reactions and clinical laboratory changes using the DMID Toxicity Grading Scale for Determining the Severity of Adverse Events provided in Protocol Attachment 3 and Section 8.1.2. This information will be relayed to the DMC and SRT, who will make recommendations regarding further conduct of the trial, and if considered necessary, may recommend pausing or stopping further administration of the investigational product. Cohort progression will only be explored if the Investigator, DMC, and SRT unanimously agree it is warranted and appropriate. These recommendations will also be communicated to the Ethics Committee and Regulatory Authority and any necessary updates will be made to the patient consent form.

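### The 85% power figure holds only for a dose with both species arms filled (n=20); a later dose may hold one arm of 10, where the planned z-test cannot reject 80% at any result

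*Combined protocol and SAP*

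**What the plan says.** SAP section 4, Sample Size Justification, states: "A one-sample z-test will have at least 85% power". The null rate is 80%, "with an alternative curative rate of 98"%, "assuming a one-sided significance level of 0.05, when the sample size is 20". The 20 comes from pooling the two parasite arms within a dose. The text then draws its conclusion for a single arm: "As such, a sample size of 10 patients per dose cohort arm was considered adequate to gain efficacy and safety data". The same sentence goes on to name evaluation of MIC and MEC, by reference to similar studies, as another ground. It gives no figures for that.

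SAP section 2, Study Design, sets the progression rule: "Cohort progression for each treatment arm will be managed independently of the other treatment arm". Its worked example has the *P. vivax* arm continuing alone to Cohorts 2B and 3B while the *P. falciparum* arm is expanded or terminated at its initial dose. Entry to Cohort 3 depends on the Cohort 2 result: "If cohort 2 proves safe (no repeated drug-related SAE) but not efficacious (crude ACPR < 60%), an adaptation will be triggered".

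Under Primary Analysis (Efficacy), no test drives the cohort decision, but a one-sample z-test of Day 14 crude ACPR against 80% is to be used for planning future studies. Planned Interim Analyses gives the decision rule as counts: 8/10 or more is success, 6/10 or 7/10 is inconclusive and leads to expansion, and 5/10 or fewer is failure.

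**The concern.** The adequacy of 10 per arm is inferred from a calculation at 20. That inference needs two arms at the dose, and the progression rule does not guarantee two arms beyond Cohort 1. The SAP gives neither power nor precision for a dose that holds one species.

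The doses concerned are those meant to inform whether boosting is needed (Cohort 2) and how an intermediate exposure performs (Cohort 3). A reader of the Sample Size Justification could carry the 85% over to them. Moreover, a non-significant z-test after 10/10 cured would look like weak evidence when it was the only outcome the test could give.

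**Working it through.** **Inputs.** From Sample Size Justification: p0 = 0.80, p1 = 0.98, one-sided alpha 0.05 (critical value 1.645), n = 20 for two pooled arms, 10 per arm. From Planned Interim Analyses: the count rule. General Approach adds that "a significance level of 0.05 will be used for all statistical tests", without giving sidedness. The true ACPR rates in step 4 are assumptions, except 98%, which is the SAP's own alternative.

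**1. The SAP's figure, n = 20.** Use the null variance for the critical value and the alternative variance for power.
- Critical proportion: 0.80 + 1.645 × √(0.80 × 0.20/20) = 0.80 + 1.645 × 0.0894 = 0.947.
- Power: Φ[(0.98 − 0.947)/√(0.98 × 0.02/20)] = Φ(0.0329/0.0313) = Φ(1.05) = 85.3%.

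This reproduces the stated figure and identifies the form of the test.

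**2. The same test, n = 10.**
- Critical proportion: 0.80 + 1.645 × √(0.16/10) = 0.80 + 1.645 × 0.1265 = 1.008, which is above 100%.
- Best possible result, 10/10: z = (1.00 − 0.80)/0.1265 = 1.58, one-sided p = 0.057. Exact binomial: 0.8^10 = 0.107.

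No result rejects 80%, so attainable power is zero at any true rate. A two-sided test, with critical value 1.96, cannot reject either. Putting n = 10 into the power formula of step 1 returns 26.3%, but that value has no meaning because the critical proportion cannot be reached. The smallest n at which an all-cured arm rejects is 11 for the z-test (z = 1.66) and 14 for the exact test (0.8^14 = 0.044).

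**3. The interval.** The SAP describes its 95% intervals by 1.96 and a margin of error. In the usual Wald form the standard error at 10/10 is √(1 × 0/10) = 0, so the interval has zero width. The exact (Clopper-Pearson) interval is 69% to 100%.

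**4. How often Cohort 1 splits.** Let s, i and f be the binomial probabilities of 8 or more, 6 or 7, and 5 or fewer cures in 10. Assume the same true rate in both species, independent arms, and the first 10 patients per arm.

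| True ACPR | s | i | f | One succeeds, other fails (2sf) | One succeeds, other inconclusive (2si) |
|---|---|---|---|---|---|
| 80% | 0.678 | 0.289 | 0.033 | 4.4% | 39% |
| 85% | 0.820 | 0.170 | 0.010 | 1.6% | 28% |
| 90% | 0.930 | 0.069 | 0.002 | 0.3% | 13% |

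At 98% in both species, s = 0.999 and exactly one arm qualifies in 2s(1 − s), about 0.2% of trials.

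The last column is not a count of single-arm doses. There the second arm is expanded, and the SAP gives neither the expanded size nor whether that arm may then join the next dose. For Cohort 3 the split depends on unboosted response rates that the documents do not give, so no frequency is offered.

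**The case against.** The strongest reply is that nothing in the SAP is miscalculated. The 85% is tied expressly to 20 patients and is right for 20; it is never claimed for a single arm of 10. The study is described as exploratory and without hypothesis testing, and the z-test is for future planning only. This stands. A reader might infer that the power figure is false, or that Cohort 2 and 3 decisions lack a valid basis. The documents support neither reading, because progression rests on observed counts.

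The plan also has two ways of raising the number. Untreated patients may be reassigned when the other arm fails, and an arm with 6/10 or 7/10 is expanded. This stands in part. Reassignment is discretionary and has no stated number or target cohort; expansion has no stated size. Neither guarantees more than 10 in an arm that scores 8/10 or better.

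A reader might also add the last two columns of the table and say that, at a true rate of 80%, about 44% of trials would have a single-species Cohort 2. The documents do not support that. Most of those trials have an inconclusive second arm whose later path is left open, and outright success-plus-failure is 4.4%. If both species truly respond at the SAP's 98%, a split at Cohort 1 is rare.

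Finally, the MIC/MEC ground is a separate reason for 10 per arm. It is stated without figures, so the power at 20 remains the only quantitative support.

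**Conclusion.** The concern holds as a gap in the sample size justification. The 85% describes a dose with both arms filled. The design allows a later dose with one arm of 10, and there the planned z-test has zero attainable power against 80%. The zero rests on the null-variance form of the test, which is the form that reproduces the SAP's figure. With the sample variance the statistic is undefined at 10/10, and 9/10 gives only z = 1.05, so that form yields no valid rejection either.

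How often this happens depends on true rates that the documents do not give and on unstated expansion and reassignment sizes. The consequence is limited to how the sample size is justified and how single-species results are reported.

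**What to change.** In Sample Size Justification, limit the power statement to doses with both species arms filled (n = 20). Add that a single-species cohort of 10 has no power against 80% and will be reported without the z-test, as an estimate with an exact (Clopper-Pearson) 95% interval (10/10: 69% to 100%) in place of the interval based on 1.96 and a margin of error.

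Support 10 per arm by the rule that is actually used. Its operating characteristics, from the binomial with n = 10, are:

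| True ACPR | Success (8 or more) | Inconclusive (6 or 7) | Failure (5 or fewer) |
|---|---|---|---|
| 60% | 17% | 47% | 37% |
| 70% | 38% | 47% | 15% |
| 80% | 68% | 29% | 3% |
| 90% | 93% | 7% | 0.2% |

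The cost is a few sentences in the SAP and a less favourable stated figure. No patients are added and no cohort rule changes.
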